1. STUDY SYNOPSIS

| |
|---|
| 
Title of Study: Phase II trial of Nivolumab and Metformin in patients with treatment refractory MSS metastatic Colorectal Cancer
 |
| 
Study Centers: Emory University Winship Cancer Institute
 |
| 
Study Phase: Phase II
 |
| 
Objectives:
 
Primary Objective:
 
▪ The primary endpoint of this study is to Evaluate the effect of metformin in combination with nivolumab on the overall response rate (ORR) (Primary Objective) as assessed by RECIST.1.1 
Secondary Objectives:
 
▪ To determine the effect of the metformin and nivolumab combination on clinical (PFS, OS) outcomes and biochemical (CEA) response.▪ To compare the effect metformin and nivolumab combination on immune and metabolic biomarkers in the tumor microenvironment and systemic circulation (pre and post treatment paired biopsies required). |
| 
Trial Design/Methodology: Single arm phase II study. 28 patients with previously treated (previously treated with fluoropyrimidine, oxaliplatin, irinotecan and EGFR inhibitor – if RAS wildtype) metastatic CRC will be started on metformin and nivolumab combination.
 
Treatment
 
1. Patients will start taking metformin 500 mg po BID for 3 days, then 500 mg am and 1000 mg pm for 4 days, then 1000 mg po bid for 1 week. Patients of the study will get paired biopsies as outlined in study calendar.2. If a patient cannot tolerate metformin 1000 mg po BID the patient will resume the metformin dose which was tolerable3. After 2 weeks of metformin only therapy (lead-in period) patients will start nivolumab 480 mg IV q4 weeks and continue metformin 1000 mg PO BID (or the tolerated dose of Metformin).4. Restaging scans will be performed at the end of cycle 2, then every 8 weeks for 2 years.5. Correlative assays will include- immune profiling of TILs and circulating lymphocytes, plasma cytokine levels and metabolic biomarkers. These will be performed at baseline at baseline, cycle 1 day 1, cycle 1 day 15, Cycle 3 Day 1 and at progression 
Treatment regimen and trial diagram:
 |

Main criteria for exclusion:

- MSI status
- Autoimmune conditions that may require systemic steroids or other immunosuppressive treatments
- Pregnancy or breast feeding

Investigational product and administration:

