6. TREATMENT PLAN

6.1.1 Agent Administration

Treatment will be administered on an outpatient basis. Reported adverse events and potential risks are described in Section 7. Appropriate dose modifications are described in Section 6. No investigational or commercial agents or therapies other than those described below may be administered with the intent to treat the patient's malignancy.

Table 1: Cycle 1 only (Day -14 through 28) Lead-in period

| Regimen Description | | | | | |
|----------------------------|-------------------------------------|-------------|--------------|-----------------|---------------------|
| Agent | Premedications ; Precautions | Dose | Route | Schedule | Cycle Length |
| | | | | | 42 days |

| | | | | | |
|------------|----------------|-----------------------------------|----|------------------------------------|--|
| Metformin | Take with food | 500 mg tablet am, 500 mg pm | PO | Twice daily D-14 through -12 | |
| Metformin | Take with food | 500 mg tablet am, 1000 mg pm | PO | Twice daily D -11 through -8 | |
| Metformin | Take with food | 1000 mg tablet am, 1000 mg pm | PO | Twice daily D -7 through -1 | |
| Metformin* | Take with food | 1000 mg tablet and, 1000 mg pm | PO | Twice daily, D1-28 | |

*If subject cannot tolerate 1000 mg po twice daily, will resume the highest tolerated dose of Metformin.

NOTE: The patient will be requested to maintain a medication diary of each dose of medication (Metformin). The medication diary ([Appendix B](#)) will be returned to clinic staff at the end of each course. Patients with diabetes mellitus will be requested to keep a blood glucose log for the first 4 weeks of the trial ([Appendix C](#))

Table 2: Cycle 2 and subsequent cycles (28 days)

| Regimen Description | | | | | |
|---------------------|------------------------------|------|-------|----------|--------------|
| Agent | Premedications ; Precautions | Dose | Route | Schedule | Cycle Length |

| | | | | | |
|------------|--|--------------------------------|--------------------|--------------------|-------------------|
| Nivolumab | Premedicate with Acetaminophen 650 mg po once prior to Nivolumab, optional | 480 mg | IV over 30 minutes | Day 1 | 28 days (4 weeks) |
| Metformin* | Take with food | 1000 mg tablet and, 1000 mg pm | PO | Twice daily, D1-28 | |

* If subject cannot tolerate 1000 mg po twice daily during Cycle 1, subject will continue the maximum tolerated dose of Metformin as in cycle 1 for the subsequent cycles.

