| Urinalysis | X | | | | | X | | | X | | | X | | | |
| T3, FT4 and TSH | X | | | | X | | | X | | | X | X | X | X | |
| ECG | X | | | | | | | | | | | | | | |

| Trial Period: | Main Study Screening (Visit 2) | Treatment Cycles ^a | | | | | | | | | | End of Treatment | Post-Treatment | | |
|---|--------------------------------|-------------------------------|-----|----------------|----------------|----------------|----------------|----------------|---------|----------------|--------------------------------|---------------------|---------------------------|-------------------------------|--------------------|
| | | 1 ^a | | 2 | 3 | 4 | 5 | 6 | 7 | 8 | To be repeated beyond 8 cycles | | Safety Follow-up | Follow Up Visits ^b | Survival Follow-Up |
| Treatment Cycle/Title: | 1 ^a | D-14 | D-7 | D1 | D15 | | | | | | | Discon | | | |
| Day | | | | | | | | | | | | | | | |
| Scheduling Window (Days): | -28 to -1 | | | ± 3 | $\pm 3^*$ | ± 3 | ± 3 | ± 3 | ± 3 | ± 3 | At time of Discon | 30 days post discon | Every 8 weeks post discon | Every 12 weeks | |
| Tumor Imaging | X | | | | | X ^g | | X ^g | | X ^g | | | | | |
| Newly Obtained Tissue Collection ^h | X | | | X ^h | X ^h | | | | | | | | | | |
| Correlative Studies Blood Collection ⁱ | X | | | X ⁱ | X ⁱ | | X ⁱ | | | | | X ⁱ | | | |

- a. Each cycle is 4 weeks, and there is 14 days lead in period in cycle 1
- b. Only for patients with ongoing treatment related toxicities
- c. Metformin will be taken 500 mg po BID for D-14 to-12, 500 mg am and 1000 mg pm for D-11 to 8, 1000 mg am and 1000 mg pm for D- 7 to -1, and continued 1000 mg BID for the rest of the study (if not able to tolerate 1000 mg BID during D1-14 period subject will be on maximum tolerated dose). Study coordinator will call the patient on Day -13 to confirm the subject is taking the right dose of medication. Nivolumab will be given after biopsy#2 (same day or up to 5 days later), and then repeated every 4 weeks.
- d. ECOG performance status should be done within 14 days or less from day 1 of cycle 1
- e. Lab results from screening may be used if completed within 1 week of day -1
- f. Baseline imaging within 4 weeks of day 1 is acceptable
- g. Scans will be done at the end of cycle 2 (± 3 days), then repeated every 2 cycles (q 8 weeks)

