- h. Paired biopsies (biopsy#1) will be obtained at baseline from all 28 patients within 28 days before Cycle 1 day 1 after consent is signed, subject #1-9, 19-23 (14 patients in total) will get post treatment biopsy (biopsy#2) cycle 1 Day 1 (same day or up to 5 days later) nivolumab will be given after biopsy#2 (same day or up to 5 days later) and subject# 10-18, 24-28 (14 patients in total) will get post treatment biopsy (biopsy#2) C1 Day 15 (same day or up to 5 days later). Most accessible metastatic disease tumor site will be biopsied by Emory Interventional Radiology. Same site will be biopsied at biopsy#1 and biopsy#2. 3 core biopsies will be obtained each time. If a patient undergoes biopsy#1 and refuse biopsy#2 this subject will be replaced. Subjects continue metformin on days of biopsy#2, and take metformin preferably 2 hours prior to the biopsy.

- i. Correlative samples will be collected at baseline, cycle 1 day 1, cycle 1 day 15, Cycle 3 Day 1 and at progression. Analysis will include phenotypic and functional analysis of T and myeloid cell subsets.

- j. Must be within 72 hours of the study drug

*Unless otherwise specified

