8.1.5.1 Screening

Screening Period

All subjects must sign an informed consent document prior to the initiation of any study related procedures. The informed consent document must be signed within 28 days of Cycle 1 Day 1. Screening procedures are to be conducted within 28 days of Cycle 1 Day 1.

- Review of study eligibility criteria
- Medical History
- Record concomitant medications taken up to 28 days prior to day 1 cycle 1
- Vitals [temperature, heart rate (HR), blood pressure (BP) and respiratory rate (RR)]
- Physical Examination, including height and weight
- ECOG Performance Status evaluation (within 14 days or less of cycle 1 day 1)
- Laboratory Assessments

- Hematology: hemoglobin, hematocrit, red blood cell count, white blood cell count with differential and platelet count
- Serum chemistry: sodium, potassium, chloride, bicarbonate, magnesium, calcium, phosphorus, blood urea nitrogen, creatinine, total bilirubin, LDH, total protein, ALP, ALT, AST, and albumin. Fasting triglycerides, cholesterol and glucose.
- Serum or urine pregnancy test for women of childbearing potential. Must be within 72 hours of study drug
- Prothrombin time (PT) and activated partial thromboplastin time (aPTT)
- Urinalysis
- Tumor markers: CEA
- T3, FT4, TSH
- 12-lead ECG
- Radiologic imaging studies to evaluate tumor status. contrast computed tomography (CT) or magnetic resonance imaging (MRI) of the chest and abdomen and pelvis. Additional imaging may be obtained as clinically indicated. Baseline scans may be done within 4 weeks prior to cycle 1 day 1.
- Baseline fresh biopsy (in all patients, 28 total) will be obtained within 28 days of day 1 cycle 1 and after consent is signed.
- Blood sample 20 cc for correlative work

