8.1.5.2 Treatment Period

8.1.5.3 Lead in Cycle 1 Day -14

- Record concomitant medications
- Vitals (temperature, HR, BP and RR)
- History and physical exam, pill diary and pill count, blood glucose log for diabetic patients
- ECOG performance status
- Toxicity assessment
- Laboratory Assessments
 - Hematology hemoglobin, hematocrit, red blood cell count, white blood cell count with differential and platelet count
 - Chemistry sodium, potassium, chloride, bicarbonate, magnesium, calcium, phosphorus, blood urea nitrogen, creatinine, glucose (random), total bilirubin, LDH, total protein, ALP, ALT, AST, and albumin
 - For the cycle1 day -1 labs, lab results from the screening tests maybe used if completed within 1 week of day -1

- Tumor marker – CEA
- Metformin

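### Baseline windows are counted from Cycle 1 Day 1 although metformin starts on Day -14, so biopsy #1 and the baseline scan may be taken on study drug

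*Combined protocol and SAP*

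**What the plan says.** **Start of study drug.** Table 1 in Section 6.1.1 opens the metformin schedule with "Twice daily D-14 through -12". Calendar footnote a adds "Each cycle is 4 weeks, and there is 14 days lead in period in cycle 1". The Synopsis makes Day 1 the first nivolumab day: "After 2 weeks of metformin only therapy (lead-in period) patients will start nivolumab 480 mg IV q4 weeks".

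**Baseline windows.** These are counted from C1D1:
- Screening in general: the calendar column runs from Day -28 to Day -1, and Section 8.1.5.1 says "Screening procedures are to be conducted within 28 days of Cycle 1 Day 1".
- Baseline scan (footnote f): "Baseline imaging within 4 weeks of day 1 is acceptable". Section 8.1.5.1 agrees.
- Biopsy #1 (footnote h, repeated in Section 8.1.3.1): "within 28 days before Cycle 1 day 1 after consent is signed". Section 8.1.5.1 gives the same 28 days.
- ECOG (footnote d): "ECOG performance status should be done within 14 days or less from day 1 of cycle 1". Sections 8.1.2.5 and 8.1.5.1 give the same limit.

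**Lab reuse.** Footnote e is attached to the Day -14 blood count and chemistry. Section 8.1.5.3, headed Day -14, says "lab results from the screening tests maybe used if completed within 1 week of day -1".

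**Items already tied to the first treatment.** Section 8.1.3.1 places the baseline research blood before study therapy begins, and Section 5.1.9 ties the pregnancy test to the first dose.

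**The concern.** Secondary objective 2 depends on tissue taken before and after treatment. Footnote h divides the second biopsy: 14 patients have it at C1D1, before nivolumab, and 14 at Cycle 1 Day 15, after nivolumab. The first group supplies the only tissue contrast that isolates metformin.

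A biopsy #1 taken between Day -7 and Day -1 is in window, but by Table 1 the patient is then scheduled for the full lead-in dose. If that patient is in the C1D1 group, both samples are on metformin, and they could be as close as Day -1 and Day 1. The pair would then say little about what metformin does and would lean towards showing no change.

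The same anchoring lets the RECIST reference scan be drug-free in some patients and on-drug in others. The ECOG and lab rules are mainly a matter of workability: a site that checks ECOG on Day -20, well before any drug, is outside footnote d.

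**Working it through.** **Step 1: day line.** Table 1 runs from Day -14 to Day -1 and then Day 1 to Day 28, with a cycle length of 42 days. Since 14 + 28 = 42, there is no Day 0.

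**Step 2: classify each permitted day against the first metformin dose on Day -14.**

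| Window | Permitted days | Before Day -14 | On Day -14 | After Day -14 |
|---|---|---|---|---|
| ECOG, 14 days before C1D1 | -14 to -1 | 0 | 1 | 13 |
| Baseline scan, 28 days | -28 to -1 | 14 | 1 | 13 |
| Biopsy #1, 28 days | -28 to -1 | 14 | 1 | 13 |
| Lab reuse, 1 week before Day -1 | -8 to -1 | 0 | 0 | 8 |

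For the scan and biopsy #1, 13/28 = 46% of the window is after the start day. If a Day 0 is assumed, the counts (before, on, after) become 13, 1 and 14 for scan and biopsy, and 0, 0 and 14 for ECOG. The conclusion is the same.

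**Step 3: visit tolerance.** The calendar allows ±3 days on Day 1, so the first metformin dose may lie 14 - 3 = 11 to 14 + 3 = 17 days before the actual Day 1. If the ECOG window is counted from the actual Day 1, a late visit (+3) puts even a pre-dose Day -14 ECOG out of window. An early visit (-3) admits 14 - 11 = 3 drug-free days. The ECOG row above is for the nominal schedule.

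**Step 4: lab rule.** Every date that the reuse rule accepts falls after the Day -14 visit whose labs it is meant to replace. Section 8.1.5.3 also speaks of labs for Day -1, but the calendar has no Day -1 visit.

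**Step 5: information lost in the C1D1 pairs.** Let the true mean paired change be δ with standard deviation s, and n = 14. The signal of a paired comparison is √n × δ/s. Assume that a fraction f of first biopsies were taken on metformin, that those pairs show no further change, and that s is unaltered. The mean change becomes (1-f)δ, the signal √n(1-f)δ/s, and the equivalent number of clean pairs n(1-f)^2.

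- f = 0: 14 × 1 = 14
- f = 25%: 14 × 0.75^2 = 14 × 0.5625 = 7.9
- f = 50%: 14 × 0.50^2 = 14 × 0.25 = 3.5

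The documents give no value for f; these are illustrations across a range.

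**The case against.** The best reply is that the intended order is plain. Biopsy #1 is described as a baseline sample and the pair as pre- and post-treatment. Imaging and the first biopsy are marked in the screening column, ahead of the Day -14 column, and recent metformin use is an exclusion (Section 5.2.2). Read that way, sites would work within about Day -28 to Day -15, and f would be small. This stands as evidence of intent and is a good reason not to assume a large f. It does not remove the rule: the windows are stated in several sections, and none makes the first metformin dose a limit for the scan or biopsy #1.

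The Day -1 in the lab rule may be a slip for another day. That is plausible, but it appears in both footnote e and Section 8.1.5.3 and still has to be reconciled.

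Section 10.2 calls the analyses hypothesis generating and gives no power for a paired comparison. That is true, so Step 5 measures lost information, not a missed design target. It also assumes no further change even for biopsies taken early in the lead-in, while the scheduled dose is still rising, and so overstates the loss for those.

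Three stronger inferences are tempting, and the documents do not support them:
- *Every compliant ECOG is on drug.* An ECOG on Day -14 before dosing meets footnote d on the nominal schedule, and Section 8.1.2.5 calls for ECOG before each dose of trial treatment.
- *The loss applies to all 28 pairs.* The Day 15 pairs would still contain nivolumab's effect, so n(1-f)^2 cannot be carried over to them.
- *The response rate is biased.* Nothing in the documents shows how much up to two weeks of metformin alone changes lesion size, so no effect on the primary decision rule can be computed.

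**Conclusion.** The concern holds as a statement of what the plan permits, not of what has happened. With metformin starting on Day -14, 13 of the 28 permitted days for biopsy #1 and the baseline scan come after the start day. The eligibility ECOG is confined, on the nominal schedule, to Day -14 or later, and the lab-reuse rule cannot work for the visit to which it is attached.

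The consequence that matters is for the metformin-only contrast in the 14 patients biopsied again at C1D1: equivalent to 7.9 clean pairs at f = 25% and 3.5 at f = 50%, under the assumptions in Step 5. If sites follow the evident intent and f is zero, nothing is lost. Any effect on the RECIST baseline is unquantified. The baseline research blood is not affected, because Section 8.1.3.1 already places it before study therapy. The point should be corrected, since an amendment of wording removes the exposure.

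**What to change.** - In footnotes d, f and h, the screening column, and Sections 8.1.3.1 and 8.1.5.1, require biopsy #1, the baseline scan and the eligibility ECOG before the first metformin dose. This takes the permitted days after the metformin start day from 13 to 0 for each. Bring the ECOG wording in Section 8.1.2.5 into line.
- In footnote e and Section 8.1.5.3, reconcile Day -1 with the Day -14 visit.
- Record the date of biopsy #1 relative to the first metformin dose. Flag any sample taken after it and exclude that sample from the main paired analysis of metformin's effect, stating this in Section 10.2. The flag remains useful if enrolment is already complete.
- Leave the baseline blood rule as it is.

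**Cost.** Amendment text and one analysis flag, with no new procedures. There is a trade-off. If the outer limit stays at 28 days before C1D1, the usable window shrinks from 28 days to 14 (Day -28 to Day -15) plus Day -14 before dosing. If the full 28 days are counted back from Day -14, a scan could be 28 + 14 = 42 days old at a C1D1 nivolumab dose, so any growth in that interval would enter the response comparison. The sponsor should choose between these openly.

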7. STUDY CALENDAR

Winship Protocol #: Winship4494-18
Protocol: Nivolumab + Metformin
Protocol/Amendment No.: Version 6/June 13, 2023
Study Flow Chart

36

| Trial Period: | | Treatment Cycles ^a | | | | | | | | | | End of Treatment | Post-Treatment | | |
|---|----------------|--------------------------------|-----|----------------|------|-----|-----|-----|-----|-----|-----|-------------------|---------------------|-------------------------------|--------------------|
| | | Main Study Screening (Visit 2) | | 1 ^a | 2 | 3 | 4 | 5 | 6 | 7 | 8 | | | | |
| Treatment Cycle/Title: | Day | D-14 | D-7 | D1 | D15 | | | | | | | Discon | Safety Follow-up | Follow Up Visits ^b | Survival Follow-Up |
| Scheduling Window (Days): | -28 to -1 | | | ± 3 | ± 3* | ± 3 | ± 3 | ± 3 | ± 3 | ± 3 | ± 3 | At time of Discon | 30 days post discon | Every 8 weeks post discon | Every 12 weeks |
| Informed Consent | X | | | | | | | | | | | | | | |
| Inclusion/Exclusion Criteria | X | | | | | | | | | | | | | | |
| Demographics and Medical History | X | | | | | | | | | | | | | | |
| Prior and Concomitant Medication Review | X | X | X | X | X | X | X | X | X | X | X | X | X | X | |
| Metformin Administration ^c | | X | X | X | X | X | X | X | X | X | X | | | | |
| Drug Diary and Pill Count (Metformin) section 13.5 ^c | | X | | X | X | X | X | X | X | X | X | X | | | |
| Blood glucose log for diabetic patients | | X | X | X | X | | | | | | | | | | |
| Nivolumab administration ^c | | | | X | | X | X | X | X | X | X | | | | |
| Post-study anticancer therapy status | | | | | | | | | | | | | X | X | |
| Survival Status | | | | | | | | | | | | | X | X | X |
| Review Adverse Events | | | X | X | X | X | X | X | X | X | X | X | X | X | |
| Full Physical Examination | X | X | | X | | X | X | X | X | X | X | | | | |
| Directed Physical Examination | | | | | X | | | | | | | | X | X | X |
| Vital Signs and Weight | X | X | | X | X | X | X | X | X | X | X | X | X | X | |
| ECOG Performance Status ^d | X ^d | X | | X | X | X | X | X | X | X | X | X | X | X | |
| Pregnancy Test – Urine or Serum β-HCG | X ^j | | | | | | | | | | | | | | |
| PT/INR and aPTT | X | | | | | | | | | | | | | | |
| CBC with Differential | X | X ^e | | X | X | X | X | X | X | X | X | X | X | X | |
| Comprehensive Serum Chemistry Panel | X | X ^e | | X | X | X | X | X | X | X | X | X | X | X | |
| Fasting triglyceride, cholesterol and glucose | X | | | | | X | | | X | | | | | | |
| CEA | | X | | X | X | | X | | X | | X | | | | |

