8.1.5.4 Cycle 1 Day -7 phone call

- Metformin
- Review of adverse events, dosing compliance and concomitant medication (by clinical trial coordinator via phone call)

8.1.5.5 Cycle 1 Day 1

- Record concomitant medications
- Vitals (temperature, HR, BP and RR)
- History and physical exam, pill diary and pill count, blood glucose log for diabetic patients
- ECOG performance status
- Toxicity assessment
- Laboratory Assessments
 - Hematology hemoglobin, hematocrit, red blood cell count, white blood cell count with differential and platelet count
 - Chemistry sodium, potassium, chloride, bicarbonate, magnesium, calcium, phosphorus, blood urea nitrogen, creatinine, glucose (random), total bilirubin, LDH, total protein, ALP, ALT, AST, and albumin
- Blood sample 20 cc for correlative work
- **Subject# 1-9, 19-23** (14 patients in total) will get biopsy#2 of paired biopsy (same day or up to 5 days later)
- Continue metformin
- Nivolumab will be started after biopsy#2 (same day or up to 5 days later).
- Nivolumab 480 mg will be administered as a 30-minute IV infusion in the infusion center. Given the variability of infusion pumps, a window of -5 minutes and +10 minutes is permitted (i.e., infusion time is 30 minutes: -5 min/+10 min).

8.1.5.6 Cycle 1 Day 15

- Record concomitant medications
- Vitals (temperature, HR, BP and RR)
- History and physical exam, pill diary and pill count, blood glucose log for diabetic patients
- ECOG performance status

- Toxicity assessment
- Laboratory Assessments
 - Hematology hemoglobin, hematocrit, red blood cell count, white blood cell count with differential and platelet count
 - Chemistry sodium, potassium, chloride, bicarbonate, magnesium, calcium, phosphorus, blood urea nitrogen, creatinine, glucose (random), total bilirubin, LDH, total protein, ALP, ALT, AST, and albumin
 - Tumor marker – CEA
- Blood sample 20 cc for correlative work
- The second half of the patients **Subject #10-18, 24-28** (14 patients in total) will get biopsy#2 of paired biopsy (same day or up to 5 days later)
- Continue metformin

8.1.5.7 Cycle 2 Day 1

- Record concomitant medications
- Vitals (temperature, HR, BP and RR)
- History and physical exam, pill diary and pill count
- ECOG performance status
- Toxicity assessment
- Laboratory Assessments
 - Hematology hemoglobin, hematocrit, red blood cell count, white blood cell count with differential and platelet count

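### The C1D15 correlative blood is not tied to the first nivolumab infusion, so its permitted post-dose interval is 1-17 days in one biopsy group and 11-17 days in the other

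*Combined protocol and SAP*

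**What the plan says.** Section 7, footnote i, sets the blood schedule by visit: "Correlative samples will be collected at baseline, cycle 1 day 1, cycle 1 day 15, Cycle 3 Day 1 and at progression". Section 8.1.3.1 repeats these five time points and uses them for T-cell and myeloid surface markers in PBMCs.

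The timing of biopsy #2 splits the patients into two groups in footnote h:

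- **Early-biopsy group:** "subject #1-9, 19-23 (14 patients in total) will get post treatment biopsy (biopsy#2) cycle 1 Day 1 (same day or up to 5 days later". For these patients the footnote adds that "nivolumab will be given after biopsy#2 (same day or up to 5 days later".
- **Later-biopsy group:** "subject# 10-18, 24-28 (14 patients in total) will get post treatment biopsy (biopsy#2) C1 Day 15 (same day or up to 5 days later".

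Section 8.1.5.5 (Cycle 1 Day 1) gives the same two allowances for the early-biopsy group: "14 patients in total) will get biopsy#2 of paired biopsy (same day or up to 5 days later", and then "Nivolumab will be started after biopsy#2 (same day or up to 5 days later". Footnote c states the nivolumab rule without limiting it to either group: "Nivolumab will be given after biopsy#2 (same day or up to 5 days later), and then repeated every 4 weeks". The flow chart places the first nivolumab in the D1 column for everyone and gives both D1 and D15 a window of ±3 days; the D15 window carries an asterisk that allows exceptions specified elsewhere.

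Neither footnote i, nor 8.1.3.1, nor 8.1.5.6 (Cycle 1 Day 15) says that the Day 15 draw moves when the first infusion moves.

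**The concern.** A sample labelled C1D15 would normally be read as two weeks after the first dose of the combination. In half the patients the first infusion may be delayed after C1D1 while the draw keeps its label, so one label can cover samples taken shortly after the infusion and samples taken two weeks after it.

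The delay is allowed because of biopsy #2, so it occurs in one biopsy group and not, on the flow-chart reading, in the other. Timing variation is then not pure noise: it is aligned with the group to which a patient's subject number assigns them.

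At stake is the interpretation of the blood markers under secondary objective 2. Section 10.2 compares each biomarker between groups formed by response or other factors and does not mention time since dosing. With 28 patients, avoidable variation in sampling time is expensive.

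**Working it through.** **Inputs, all from the protocol**

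- Early-biopsy group, subjects 1-9 and 19-23: 9 + 5 = 14. Later-biopsy group, subjects 10-18 and 24-28: 9 + 5 = 14. This reproduces the stated 14 and 14, and together they cover subjects 1-28. Nine of the first 18 patients are in the early-biopsy group.
- Biopsy #2 in the early-biopsy group: 0 to 5 days after C1D1 (footnote h, 8.1.5.5).
- First nivolumab: 0 to 5 days after biopsy #2 (footnotes c and h, 8.1.5.5).
- Day 15 window: ±3 days (flow chart).

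The protocol states no interval from nivolumab to blood, so there is no figure of its own to reproduce for that.

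**Can C1D1 simply mean the infusion day?** Not in the early-biopsy group. Biopsy #2 may fall up to 5 days after C1D1 and must precede nivolumab. Whenever that allowance is used, C1D1 is earlier than the infusion.

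**Day of first nivolumab, early-biopsy group**

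- Earliest: Day 1.
- Latest, windows in sequence: 1 + 5 + 5 = Day 11, which is 10 days after C1D1.
- Latest, one shared allowance: 1 + 5 = Day 6, which is 5 days after C1D1.

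**Day of blood:** 15 − 3 = Day 12 to 15 + 3 = Day 18.

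**Interval = day of blood − day of first nivolumab**

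| First nivolumab | Blood exactly on Day 15 | Blood on Day 12-18 |
|---|---|---|
| Day 1 | 14 | 11-17 |
| Day 6 | 9 | 6-12 |
| Day 11 | 4 | 1-7 |

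Permitted range by group, in days:

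- Early-biopsy group, windows in sequence: 12 − 11 = 1 to 18 − 1 = 17.
- Early-biopsy group, one shared allowance: 12 − 6 = 6 to 18 − 1 = 17.
- Later-biopsy group, dosed on Day 1 as in the flow chart: 12 − 1 = 11 to 18 − 1 = 17.

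**Sensitivity to two other readings**

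- If the ±3 days on C1D1 is also applied against a nominal calendar, the early-biopsy range is 12 − (1 + 3 + 5 + 5) = −2 to 18 − (1 − 3) = 20 days. The later-biopsy range is 12 − (1 + 3) = 8 to 18 − (1 − 3) = 20 days. The groups still differ.
- If footnote c is applied literally to the later-biopsy group, first nivolumab falls between Day 15 and Day 15 + 5 + 5 = Day 25. The C1D15 blood then lies between 12 − 25 = 13 days before and 18 − 15 = 3 days after it. That contradicts the nivolumab entry at D1 in the flow chart, so the passages must be reconciled.

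**If the draw were set at 14 ± 3 days after the recorded first infusion:** 14 − 3 = 11 to 14 + 3 = 17 days in both groups.

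**The case against.** The strongest reply is that the short end of the range is an extreme. It needs the full biopsy allowance, the full nivolumab allowance and a draw three days early, all in the same patient. The text does not settle whether the two allowances run in sequence or are one, and no sentence says that Day 15 is counted from C1D1; that is inferred from the visit label and from the absence of any other anchor. This stands as a limit on size. It does not remove the problem, because the shared-allowance reading still gives 6-17 days.

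Four stronger readings are tempting, and the documents do not support them:

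- **That this is the only early sample on the combination.** It is the only correlative blood with a fixed date between first nivolumab and C3D1. On the flow-chart reading, biopsy #2 in the later-biopsy group is also early on-combination tissue.
- **That objective 2 reads an early drug effect from this one draw.** Objective 2 names no early effect, the plan lists five blood time points, and 8.1.3.1 places the PBMC functional assays at baseline and week 10. Footnote i is less specific, but phenotyping is chiefly affected.
- **That a planned comparison is biased.** No comparison of blood markers between the two biopsy groups is specified. Biopsy group could enter only as one of the unnamed other factors in section 10.2, which calls its analyses hypothesis generating.
- **That the CEA endpoint is compromised.** CEA is drawn at the same visit, but it is also drawn at later cycles, and nothing makes C1D15 the point at which biochemical response is judged.

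**Conclusion.** The point holds in a limited form. Followed exactly, the schedule permits first nivolumab up to 10 days after C1D1 (5 on the shared-allowance reading) in 14 of 28 patients, with nothing linking the C1D15 blood to that infusion. The permitted post-dose interval is 1-17 days (or 6-17) in that group and 11-17 days in the other.

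This rests on three assumptions: Day 15 is counted from C1D1, C1D1 itself is fixed, and the flow chart prevails over footnote c for subjects 10-18 and 24-28. The ranges are what the rules allow. The documents give no basis for saying how often the allowances will be used.

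The consequence is added timing variation, aligned with biopsy group, in one blood sample of a secondary, exploratory objective. A reader might infer that the trial's efficacy conclusion is at risk; it is not, since neither the ORR test nor the two-stage rule uses this sample. The matter is still worth correcting, because the remedy is cheap and the variation cannot be accounted for unless the dates are used.

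**What to change.** 1. **Analysis (section 10.2).** Record the dates of the first nivolumab infusion and of each correlative draw. Analyse the C1D15 blood markers by actual days since first nivolumab, and report the distribution of that interval by biopsy group. This adds no procedure and remains possible after enrolment has ended, provided both dates were recorded.
2. **Sampling (footnote i, 8.1.3.1, 8.1.5.6).** Where feasible, define the C1D15 correlative draw as 14 days (±3) after the recorded first infusion.
3. **Pre-dose sample (footnote i, 8.1.3.1, 8.1.5.5).** State that the C1D1 correlative blood is taken before the first infusion. The order of items in 8.1.5.5 suggests this but does not require it.
4. **Definitions.** Reconcile footnotes c and h, the flow chart and 8.1.5.5 so that C1D1 has one meaning, and say whether the two 5-day allowances run in sequence. Which treatment timing is intended is for the sponsor to state; this point proposes none.

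The cost lies in step 2. The Day 15 visit also carries the toxicity assessment and safety laboratory tests. If that visit stays fixed, some patients in the early-biopsy group may need a separate draw, up to 10 days later than now scheduled. If the whole visit moves, so does the timing of the safety assessments. If neither is acceptable, step 1 alone recovers much of the benefit.
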